9 STUDY ADMINISTRATION, DATA HANDLING AND RECORD KEEPING	14

CONFIDENTIAL

8.4.1	Follow-up report	13
8.5	MEDICAL MONITORING.....	13
9.1	CONFIDENTIALITY, DATA COLLECTION/MANAGEMENT, & RECORDS RETENTION.....	14
10	STUDY MONITORING, AUDITING, AND INSPECTING	14
10.1	STUDY MONITORING PLAN.....	14
10.2	AUDITING AND INSPECTING.....	14
11	ETHICAL CONSIDERATIONS	14
11.1	RISKS	15
11.2	BENEFITS	16
11.3	RISK BENEFIT ASSESSMENT	16
11.4	INFORMED CONSENT PROCESS / HIPAA AUTHORIZATION.....	16
12	STUDY FINANCES	16
12.1	FUNDING SOURCE.....	16
12.2	CONFLICT OF INTEREST.....	17
12.3	SUBJECT STIPENDS OR PAYMENTS.....	17

CONFIDENTIAL

This material is the property of the University of Pennsylvania.

List of Abbreviations

For example: LIST OF ABBREVIATIONS-list alphabetically.

AE: Adverse event

DLPFC: Dorsolateral Prefrontal Cortex

DMC: Data Monitoring Committee

DM: Diabetes Mellitus

ECG: Electrocardiogram

IAPS: International Affective Picture System

iTBS: Intermittent Theta-Burst Stimulation

MADRS: Montgomery-Asberg Depression Rating Scale

MRI: Magnetic Resonance Imaging

RMT: Resting Motor Threshold

rTMS: Repetitive Transcranial Magnetic Stimulation

SST: Sternberg Sort Task

TMS: Transcranial Magnetic Stimulation

Study Summary

Title	Task Augmentation of TMS
Short Title	Task TMS
IRB Number	832232
Protocol Number	N/A
Phase	IND Exempt
Study Duration	2 years
Study Center(s)	Single-center

Objectives

Overall objectives

In this R01 proposal we will determine what neural systems underlie TMS-evoked brain responses and how the addition of a task organizes and augments this response to induce plasticity. We first determine which tasks known to activate DLPFC alone or in combination with TMS have greater activation of the DLPFC and have maximal anti-correlation with the subgenual cingulate. In addition, tasks will be combined with TMS in a sham controlled double-blind experiment to test neuromodulation-induced effects. In a sample of 25 healthy participants we will conduct a series of experiments to examine task effects, task-specific TMS augmentation effects and task-specific augmentation of TMS neuromodulation.

Primary outcome variable(s)

We will determine both an “intensity (difficulty) effect” and an “emotion effect” of task-induced fMRI activity in the scanner, collecting these measures in the same subjects. Participants will receive two working memory tasks:

1a) Sternberg Sorting Task (SST): a cognitive task comparing low-load vs. high-load conditions in which the picture stimuli are letters.

1b) International Affective Picture System (IAPS): an emotional task using IAPS picture that will also compare low load and high load conditions. The number of images will vary by condition load, but for both the high-load & low-load conditions, participants will look at IAPS pictures and answer questions about the images. Further, jittered within this design will be both neutral and negative blocks of IAPS pictures.

Secondary outcome variable(s)

Aim 2: to determine which task provides greater augmentation of the TMS-induced DLPFC activation, participants will receive in randomized order:

- 1) The cognitive SST working memory task or the IAPS task alone
- 2) rTMS + the cognitive SST working memory task or rTMS + the IAPS emotional task in randomized order. rTMS and the cognitive tasks will be conducted in the fMRI scanner where brain activation to a TMS probe and connectivity will be obtained.
- 3) rTMS alone

Aim 3: to determine the effect of neuromodulation on DLPFC activation healthy participants will be randomized to one of the 3 task conditions: high-load cognitive SST, high-load IAPS task, or low-load SST (sham task condition). Following a 4 session course (2 session separated by at least 4 hours on one day, followed by 2 sessions separated by at least 4 hours on a second day) of either active rTMS or sham TMS neuromodulation in combination with the task condition participants will again have probe sessions in the scanner where DLPFC activation and connectivity will be determined. Following a 2-week interval, participants will receive the other stimulation condition (sham TMS if active first and active TMS if sham first).

CONFIDENTIAL

Number of Subjects 25

Key inclusion criteria

Gender, inclusive
18 – 60 years of age
Right-handed
No history of meeting DSM criteria for any diagnosis
Normal cognition
Patients must be able to read and understand English
Participants must be able to provide consent

**Main Inclusion and
Exclusion Criteria**

Key exclusion criteria

Pregnancy (Female participants)
Outside age range
Meets DSM criteria for any diagnosis
Unable to have an MRI scan
Medical condition that interferes with the collection or interpretation of MRI data
Implanted devices such as: aneurysm clip or cardiac pacemaker
History of stroke, epilepsy, or brain scarring
Cognitive impairment
Recent use of psychoactive medications, as determined by investigators
Otherwise determined by investigator to be unfit for participation:
ex) meets DSM criteria for current alcohol or substance use disorder (in last 3 months)

**Investigational
Product (drug,
biologic, device, etc.)**

**For Device include
the planned use**

MagVenture X100 Stimulator - *please refer to the 'Devices in Research Form' attached to this submission*

**For Drug, food,
cosmetic, etc.**

MagVenture Cool B65 Coil - *please refer to the 'Devices in Research Form' attached to this submission*

include the dose,

route of

administration and

dose regimen

MagVenture MRI B91 Coil - *please refer to the 'Devices in Research Form' attached to this submission*

CONFIDENTIAL

This material is the property of the University of Pennsylvania.

Duration of administration (if applicable)	The neuromodulation participants will receive is FDA-approved iTBS at 120% RMT stimulation intensity; triplet 50 Hz bursts, repeated at 5 Hz; 2 s on and 8 s off; 600 pulses per session; for a total duration of 3 min 9 s per session to the 'Fitzgerald Target' (identified via MRI imaging). Sham TMS will also be administered at the aforementioned parameters.
Reference therapy	When in the scanner, participants will receive single pulse TMS probes while completing tasks at 120% RMT with 77 total pulses.
Statistical Methodology	Efficacy within subjects: Repeated measures ANOVA will be used to assess changes from baseline to post-stimulation for each task condition. Efficacy between subjects: neuro-response rates and time to response will be compared with published rates within the literature to extrapolate the significance of this modality.
Safety Evaluations	No data or safety monitoring board will be necessary for this protocol. The principal investigator will be responsible for monitoring this protocol.
Data and Safety Monitoring Plan	No data or safety monitoring board will be necessary for this protocol. The principal investigator will be responsible for monitoring this protocol.

CONFIDENTIAL

This material is the property of the University of Pennsylvania.

BACKGROUND AND STUDY RATIONALE

This study will be conducted in full accordance all applicable University of Pennsylvania Research Policies and Procedures and all applicable Federal and state laws and regulations including [as applicable include the following regulations as they apply 45 CFR 46, 21 CFR Parts 50, 54, 56, 312, 314 and 812 and Good Clinical Practice: Consolidated Guidelines approved by the International Conference on Harmonisation (ICH). Note: Only include ICH compliance if the study will actually comply with these requirements.] All episodes of noncompliance will be documented.

Introduction

This should include a brief paragraph or two that describes rationale for the study.

1.1 Background and Relevant Literature

The standard clinical technique for using repetitive transcranial magnetic stimulation (rTMS) for major depressive disorder (MDD) is associated with limited efficacy to date (Lefaucheur 2014; Berlim 2014). Among the potential causes of limited efficacy are the scalp based targeting technique that is currently the most common targeting method rather than techniques that incorporate fMRI-neuronavigation, which have been shown to have greater efficacy (Fitzgerald 2009a). Image guided TMS can target specific functional brain networks with greater resolution that takes into account individual differences in brain anatomy. Another technique for improving treatment efficacy may be to combine it with cognitive activation of the DLPFC designed to activate the same neural circuitry that is targeted by TMS. Cognitive paired associative stimulation builds on the well-established paradigm of paired associative stimulation (PAS). In that paradigm, co-activation of sensorimotor cortex with afferent stimulation of the median nerve timed to arrive as a TMS pulse is delivered to motor cortex, has been shown to increase cortical response to subsequent stimuli (Ziemann 2008). Analogously, simultaneous activation by 2 neurostimuli (TMS to DLPFC and task activating DLPFC) could result in greater cortical activation and have a greater effect on executive function cognitive control than either stimulus alone. Several studies now suggest that the brain "set" is critical in determining TMS effect (McKinley et al) and that simultaneous task activation can augment TMS efficacy (Li et al). It is not known whether the specific mode of cognitive activation is critical or whether the absolute amplitude of activation is more important. One theory proposes that tasks that activate the DLPFC promotion system via priming will maximally augment TMS treatment (Strauman 2013; Detloff & Strauman 2016), suggesting that the nature of the task is critical in TMS augmentation. Another set of observations (McTeague et al 2018) has found that magnitude but not the valence of emotional arousal predicted TMS augmentation. This suggests that it may not be task type but rather magnitude of emotional arousal that influences maximal TMS treatment augmentation.

Significance: this protocol builds on the RDoC construct of cognitive control to assess the neural substrates involved in TMS activation as well as task-induced TMS augmentation. By using both a passive vs active version of the SST working memory task we can examine the effect of manipulation characteristics of tasks and by using cognitive vs. emotional versions of the task we can probe the contribution of emotional arousal to the effects. Further by randomizing subjects to one of three task conditions (including a task control condition) we can determine the effect of task augmentation on TMS.

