3.1 Primary Objective

We will determine both an “intensity (difficulty) effect” and an “emotion effect” of task-induced fMRI activity in the scanner, collecting these measures in the same subjects. Participants will receive two working memory tasks:

1a) Sternberg Sorting Task (SST): a cognitive task comparing low-load vs. high-load conditions in which the picture stimuli are letters.

1b) International Affective Picture System (IAPS): an emotional task using IAPS picture that will also compare low load and high load conditions. The number of images will vary by condition load, but for both the high-load & low-load conditions, participants will look at IAPS pictures and answer questions about the images. Further, jittered within this design will be both neutral and negative blocks of IAPS pictures.

We will compare low-load vs. high-load brain activation and connectivity in the cognitive vs. emotional tasks.

Hypothesis 1a: Compared with the maintenance (low-load) SST condition, the high-load cognitive SST condition will produce greater DLPFC activation and dIPFC/sgACC anticorrelation.

Hypothesis 1b: Compared with the low-load IAPS emotional task, the high-load IAPS emotional pictures will produce higher activity in the DLPFC and dIPFC/sgACC anticorrelation.

Hypothesis 1c: The picture rating for arousal will be correlated with the activity in the DLPFC and dIPFC/sgACC anticorrelation.

Secondary Objectives:

Aim 2: to determine which task provides greater augmentation of the TMS-induced DLPFC activation, participants will receive in randomized order:

- 1) The cognitive SST working memory task or the IAPS task alone
- 2) rTMS + the cognitive SST working memory task or rTMS + the IAPS emotional task in randomized order. rTMS and the cognitive tasks will be conducted in the fMRI scanner where brain activation to a TMS probe and connectivity will be obtained.
- 3) rTMS alone

Hypothesis 2a: rTMS + either task will have greater DLPFC activation and greater dIPFC/sgACC anticorrelation than rTMS alone.

Hypothesis 2b: rTMS + the IAPS emotional working memory task will have greater DLPFC activation and greater dIPFC/sgACC anticorrelation than rTMS + cognitive SST (more robust)

Hypothesis 2c: rTMS + IAPS emotional task will have greater signal to noise (more selective).

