Aim 3: to determine the effect of neuromodulation on DLPFC activation healthy participants will be randomized to one of the 3 task conditions: high-load cognitive SST, high-load IAPS task, or low-load SST (sham task condition). Following a 4 session course (2 session separated by at least 4 hours on one day, followed by 2 sessions separated by at least 4 hours on a second day) of either active rTMS or sham TMS neuromodulation in combination with the task condition participants will again have probe sessions in the scanner where DLPFC activation and connectivity will be determined. Following a 2-week interval, participants will receive the other stimulation condition (sham TMS if active first and active TMS if sham first).

[figure not shown]
Hypothesis 3a: Task (any of the 3) + active rTMS will result in greater DLPFC activation and greater dIPFC/sgACC anticorrelation than task plus sham rTMS

Hypothesis 3b: the IAPS task in combination with active rTMS will produce greater activation than the cognitive SST + active TMS or than control task + active TMS.

CONFIDENTIAL

4 Investigational Plan

Below is an example of the proposed study flow after screening visit. Please refer to attached task descriptions for further information:

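### Load is described as a different manipulation in the SST and the IAPS task, so IAPS-versus-SST contrasts cannot isolate emotional arousal

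*Combined protocol and SAP*

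**What the plan says.** **SST load.** The Significance paragraph in section 1.1 gives the purpose of the SST contrast: "By using both a passive vs active version of the SST working memory task we can examine the effect of manipulation characteristics of tasks". In section 3.1, Hypothesis 1a identifies the low level as maintenance: "Compared with the maintenance (low-load) SST condition, the high-load cognitive SST condition will produce greater DLPFC activation". The stimuli are letters.

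**IAPS load.** Section 3.1, item 1b: "The number of images will vary by condition load, but for both the high-load & low-load conditions, participants will look at IAPS pictures". The sentence goes on to say that questions about the pictures are answered. Neutral and negative blocks are included within this task.

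**Use of the two tasks together.** Section 3.1 labels load as an intensity or difficulty effect and then plans a comparison across tasks: "We will compare low-load vs. high-load brain activation and connectivity in the cognitive vs. emotional tasks". Hypothesis 2b expects rTMS with the IAPS task to exceed rTMS with the SST. In Aim 3 the arms are high-load SST, high-load IAPS and low-load SST as the sham task. Hypothesis 3b expects that "the IAPS task in combination with active rTMS will produce greater activation than the cognitive SST + active TMS", and also that IAPS exceeds the control task. The Significance paragraph presents the two tasks as a cognitive and an emotional version of one task and says their contrast probes what emotional arousal contributes.

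**Analysis.** Section 8 specifies a repeated measures ANOVA of change from baseline to post-stimulation for each task condition. It names no performance measure and no adjustment for difficulty.

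**The concern.** To attribute a difference between two tasks to emotion, the tasks should agree in everything else that could drive DLPFC activity. As described, they differ in at least two other respects. The stimuli are letters in one and pictures in the other. The load step is a change of operation in one and a change of quantity in the other. A third respect, difficulty, is left open.

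A larger load effect in the IAPS task could then reflect adding pictures rather than changing the operation. An IAPS advantage in Hypothesis 2b or 3b could reflect stimulus, operation or effort. Section 1.1 asks whether the mode of cognitive activation or its absolute amplitude matters for augmenting TMS. A task contrast in which both may vary cannot settle that question, and a paper following the plan could credit arousal with a difference that has other explanations.

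**Working it through.** There is no figure in the plan to reproduce. Section 5.5 gives 25 participants, and no alpha, SD, effect size or power is stated. The check is therefore mainly a comparison of definitions.

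**Step 1: set the definitions side by side.**

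| Feature | SST | IAPS task | Source |
|---|---|---|---|
| Stimulus | Letters | Affective pictures | 3.1, items 1a and 1b |
| Low load | Maintenance (passive) | A different number of images from high load | 1.1; 3.1 |
| High load | Active version; manipulation is inferred | A different number of images from low load | 1.1; 3.1 |
| Activity | Changes with load | Viewing and answering questions at both loads | 1.1; 3.1 |
| Set sizes, calibration, accuracy or reaction time | Not described | Not described | 3.1, 6, 7, 8 |

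That high-load SST means active manipulation is an inference. Section 3.1 does not define it, but the passive/active wording, the reference to manipulation and the maintenance label all point that way.

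**Step 2: go through the hypotheses.**

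- 1a and 1b: high versus low load within one task. No cross-task matching is needed, so they are unaffected.
- 1c: arousal rating against activity. It does not depend on the SST.
- Aim 1 cross-task load comparison: the difference of two load effects, each produced by a different manipulation. Affected.
- 2b: rTMS with IAPS against rTMS with SST. Emotion, stimulus and operation differ together. Affected.
- 3b: high-load IAPS against high-load SST has the same problem. High-load IAPS against low-load SST also adds the nominal load level, and there is no low-load IAPS arm to separate it. Affected.

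**Step 3: illustrate what a difficulty offset could do, for raw-level comparisons only.** Assumptions, none from the documents: no true emotion effect, two-sided 5% t tests, and a constant difficulty offset that happens to favour IAPS. The probability is that of a significant result favouring IAPS, which is 0.025 with no offset.

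- Hypothesis 2b, paired, n = 25, within-person correlation ρ: standardised effect = offset / √(2(1 − ρ)), noncentrality = effect × √25, 24 df.
 - Offset 0.3 SD: ρ = 0.5 gives effect 0.30, noncentrality 1.5, probability 0.30; ρ = 0.7 gives 0.387, 1.94, probability 0.46.
 - Offset 0.5 SD: ρ = 0.5 gives 0.50, 2.5, probability 0.67; ρ = 0.7 gives 0.645, 3.23, probability 0.87.
- Hypothesis 3b, two arms of 8 (25/3 ≈ 8.3; equal allocation assumed): noncentrality = offset × √(8/2), 14 df.
 - Offset 0.5 SD: noncentrality 1.0, probability 0.15. Offset 1.0 SD: noncentrality 2.0, probability 0.46.

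**Step 4: ask whether those figures apply to the planned analysis.** Write a participant's activation in task k as level a_k plus stimulation effect s_k. Post minus baseline is (a_k + s_k) − a_k = s_k. Active minus sham, which each person receives in the crossover, also removes a_k, and so does rTMS plus task minus task alone in Aim 2. A constant offset in a_k therefore drops out of each of these contrasts. Only a difference between tasks in s_k remains. The Step 3 figures hold only if activation levels are compared directly, as Hypotheses 2b and 3b are worded. They do not describe the change analysis in section 8.

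The attribution problem survives the subtraction: s_k can differ because of stimulus or operation as well as emotion.

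**The case against.** **The task details are elsewhere.** Section 4 refers to attached task descriptions that were not available for this review. Set sizes, the high-load operation or a difficulty calibration may be there. This stands as a limit: a reader might infer that one task is harder than the other, or that difficulty was never matched, and the documents support neither. They show only that the protocol text describes no matching.

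**The definitions may be over-read.** Item 1b does not say that nothing but image number changes, and high-load SST is undefined in section 3.1. This also stands in part. The two descriptions nevertheless differ as printed, and nothing in the text makes them equivalent.

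**Aims 2 and 3 ask which task works better.** If a harder task augments TMS more, that is a valid answer to the whole-task question and not a false positive. This is right, and it is why the remedy is to state that reading. It does not rescue the Significance paragraph, which goes further and attributes the contrast to arousal.

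**Emotion can be studied inside the IAPS task.** Negative and neutral blocks and the ratings in Hypothesis 1c need no SST match. This is correct, although no hypothesis uses the negative-versus-neutral contrast.

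**The error probabilities overstate the risk.** A reader might take 0.30 to 0.87 as the false-positive rate of Hypothesis 2b. It is not: the offsets have no source in the documents, the analysis in section 8 would remove a constant offset, and if the SST is the harder task the bias runs against Hypotheses 2b and 3b.

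**Conclusion.** The concern holds as a limit on interpretation. Load is described as a change of operation in the SST and a change of image number in the IAPS task, and the protocol text describes no matching or measurement of difficulty. The Aim 1 cross-task load comparison and Hypotheses 2b and 3b confound emotion with operation and stimulus, and possibly with difficulty. They can show that two tasks differ; they cannot show that arousal is the reason.

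No size can be put on the bias from the documents. The conclusion rests on the printed descriptions and on the inference that high-load SST involves manipulation. If the attached descriptions show a matched load step and calibrated difficulty, those parts fall away. The difference between letters and pictures would remain.

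**What to change.** 1. In section 3.1, state that the Aim 1 cross-task load contrast and Hypotheses 2b and 3b compare two whole tasks that differ in stimulus and in how load is set.
2. In the Significance paragraph of section 1.1, remove the claim that the cognitive-versus-emotional contrast probes the contribution of emotional arousal.
3. Name the within-IAPS evidence as the source for any emotion effect: negative versus neutral blocks, added to section 8 as a stated contrast, and the arousal ratings of Hypothesis 1c.
4. Report accuracy by task and load as a descriptive check on difficulty. This assumes the responses are recorded and can be scored, which the protocol text does not say.
5. Quote the probabilities above, if at all, only as illustrations for raw-level comparisons with the direction of any offset unknown.

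This needs no extra participants or scans. The downside is a narrower stated conclusion. Rebuilding the IAPS task as a picture version of the SST would go further, but it is a different experiment, would need piloting, and is not required to correct the claim.

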1.2 Name and Description of the Investigational Product

IDE Exempt

2 Study Objectives

- 3 This protocol aims to determine what neural systems underlie TMS-evoked brain responses and how the addition of a task organizes and augments this response to induce plasticity. We first determine which tasks known to activate DLPFC alone or in combination with TMS have greater activation of the DLPFC and have maximal anti-correlation with the subgenual cingulate. In addition, tasks will be combined with TMS in a sham controlled double-blind experiment to test neuromodulation-induced effects. In a sample of 25 healthy participants we will conduct a series of experiments to examine

CONFIDENTIAL

task effects, task-specific TMS augmentation effects and task-specific augmentation of TMS neuromodulation.

